6 STATISTICAL PLAN AND METHODS

A reduced subset of materials will be provided for the first DSMB while formal TLFs are created. The materials for the first DSMB will consist of Excel spreadsheets extracted from the clinical database. The spreadsheets will have variable labels as column headers and will be filtered to allow easy examination. Domains to be provided to the first DSMB include disposition, demographics, medical history, concomitant medications, adverse events, and laboratory results for blood chemistry, hematology, and urinalysis. Additionally, pivot tables counting adverse events by system organ class and preferred term and by system organ class, preferred term, and severity will be created for the following subsets of adverse events: local systemic solicited adverse events, unsolicited adverse events, serious adverse events, and adverse events leading to vaccine discontinuation.

6.1 Background Characteristics

6.1.1 Subject Disposition

A summary of subject disposition will be provided.

The count of subjects in the AEC will be presented along with subject who received the placebo. Additionally, there will be counts for subjects completing receiving vaccination #1, completing

vaccination #2, discontinuing from vaccination, the reasons for not completing the vaccination, completing the study, and the reasons for not completing the study.

6.1.2 Demographics and Baseline Characteristics

A summary of demographics and baseline characteristics will be provided. The demographics portion of the summary will include age, gender, race, ethnicity, baseline height, baseline body weight, and baseline BMI. Additionally, baseline lab results for hepatitis B, hepatitis C, and HIV will be presented.

6.1.3 Medical History

A summary of medical history will be provided. Any pre-existing conditions or signs/symptoms noted via interview or medical records prior to first study injection will be presented by system organ class using the Medical Dictionary for Regulatory Affairs® (MedDRA) Version 25.0.

6.1.4 Prior and Concomitant Medication

Each medication will be coded to a preferred term and an Anatomic Therapeutic Classification (ATC) code using the World Health Organization (WHO) Drug Dictionary. Prior medications are defined as medications that are stopped before the first vaccination dose. Concomitant medications are defined as those medications with a start date on or after the vaccination dose of study drug or the medications started before the dose and continued during the vaccination period. The number and percentage of subjects taking each prior or concomitant medication will be displayed by medication class (anatomical classification) and preferred term for each treatment group. Details for imputing missing or partial start and/or stop dates of medication are described in Section 5.4.

6.2 Extent of Exposure and Treatment compliance

A full course of study product administration consists of one or two doses of vaccine in each study vaccination period. A summary table detailing the total number of doses received will be presented by treatment compliance.

6.3 Safety Analyses

6.3.1 Adverse Events (AEs)

6.3.1.1 General Guidance on AEs

All AE related Tables and Listings will be analyzed using the SC. All adverse-events in the SC will be presented in listings. Only Treatment-Emergent Adverse Events (TEAEs) will be summarized in tables. TEAEs include: 1) AEs with an onset on or after the first vaccination dose and 2) AEs that worsen relative to the pre-treatment state. The period of observation for collection of TEAEs extends from the time the participant receives the first dose of vaccine through the last study visit.

Adverse events will be coded to the System Organ Class (SOC) and preferred term (PT) level using the Medical Dictionary for Regulatory Affairs (MedDRA dictionary).

TEAEs missing severity will be summarized as “missing” in summary tables.

The summary tables for unsolicited AEs will use the following algorithms for counting the subject:

- System Organ Class row: Subjects experiencing the same AE System Organ Class several times will only be counted once.
- Preferred term row: Subjects experiencing the same AE preferred term several times with different grades will only be counted once with the maximum grade.
- Any event row: Each subject with at least one adverse event will be counted only once at the maximum grade no matter how many events they have.

Unless otherwise stated, AEs will be ordered alphabetically by SOC and in descending order of frequency by PT.

The summary tables for the rate and severity of solicited AEs will be presented by the terms defined on the eCRF.

Other types of events collected are defined as follows:

- 1) Medically-Attended Adverse Events (MAAE) – A condition prompting emergency room visit, physician visit not related to a common disease/not a routine visit or an SAE not related to a common disease SAE.
- 2) Serious Adverse Event (SAE) – Any untoward medical occurrence that *at any dose* results in death, is life-threatening, requires hospitalization or prolongation of existing hospitalization, results in disability/incapacity, is a congenital abnormality/birth defect in an offspring of a study participant, or is another medically important event.

6.3.1.2 AE Summaries

An overview summary of TEAEs including:

- 1) Counts and percentages of subjects
 - a. With any TEAE,
 - b. With any local solicited AEs during 7 days of vaccination dosing,
 - c. With any systemic solicited AEs during 7 days of vaccination dosing,
 - d. With any unsolicited AEs within 28 days of each vaccination dose,
 - e. With any unsolicited MAAEs at Day 56 and 28 days after each vaccination dose,
 - f. With any unsolicited SAEs at Day 56 and 28 days after vaccination dose,
 - g. With any unsolicited AEs leading to discontinuation of study vaccination,
 - h. With any unsolicited AEs leading to study discontinuation,
 - i. With any unsolicited AEs during the study,

j. With any unsolicited SAEs during the study.
will be presented stratified by treatment and age group.

For each type of AE noted in the overall summary point 2 except solicited AEs (2b and 2c), we will additionally produce summaries of the AEs by SOC and PT. Furthermore, summaries of event types 2d, and 2i will be presented for by SOC, PT, and severity (mild/moderate/severe/potentially life threatening).

Solicited AEs will be summarized separately for local AEs, systemic AEs, and fever >38 centigrade as collected on the solicited AEs eCRF pages. These summaries will be presented for each dose separately and cumulatively, will count the number of subjects experiencing at least one solicited AE, and will count the number of subjects experiencing at least one of each of the solicited AEs ordered per the solicited AEs eCRF pages.

Lastly, within the solicited AE by SOC/PT summary, 2-sided, alpha=0.05 Fisher's Exact tests will be performed to assess differences in rates of these adverse events between the treatment groups. No adjustment will be made to account for multiplicity of tests performed.

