	
number of IFN-γ ELISPOT-positive cells per 10^6 PBMCs. Immunogenicity results will be presented descriptively as point estimates and 95% confidence intervals (CIs), which will be tabulated by study group. Exploratory immunogenicity endpoints may include additional markers for T cell responses by ELISPOT and serum binding IgG subclasses as a marker of Th1 (IgG1 and IgG3) and Th2 (IgG4) dominated responses. The immunogenicity population will include all participants who receive the prescribed study vaccine or placebo and underwent at least one immunogenicity assessment after vaccination.
 
The total amount of blood to be drawn for clinical laboratory tests, and immunology evaluations is approximately 15-20 mL for initial (pre-vaccination) blood draw, and approximately 55-60 mL for subsequent blood draws.
 
Protection of Participants Informed Consent
 
The study protocol, informed consent form, and other study related documentation will be reviewed and approved by the local research ethics board (REB). Written informed consent will be obtained after participants have read the approved informed consent form, have had adequate opportunity to discuss the study with an investigator or a qualified designee and before the initiation of any study related procedures.
 
Data Safety Monitoring Board (DSMB)
 
While the trial is ongoing, to allow regular review of the accumulated safety data, a DSMB will be established to perform early review of blinded post-vaccination safety data 7 and 28 days after each vaccination (solicited and unsolicited AEs and safety labs), and regularly thereafter through study termination. Second vaccinations will only be administered after the DSMB confirmation that safety after the first dose is acceptable and that stopping rules have not been met. The DSMB may recommend to continue, pause, modify, or suspend the further enrollment to the study.
 
Stopping Rules
 
The stopping rules are proposed as conditions that would stop further vaccinations in an individual subject (at any dose level) if they experience any of the following events that are assessed as possibly related by the investigator, or for which there is no alternative, plausible, attributable cause
 
• Grade 4 local (injection site) or systemic solicited AE within 7 days after any study injection• Fever $>40.0^{\circ}\text{C}$ ($>104.0^{\circ}\text{F}$) for at least 1 daily measurement within 7 days after vaccination• Any grade 4 or life-threatening event within 7 days after any study injection, regardless of relationship to study vaccine• Clinically significant systemic reaction (i.e., angioedema, generalized urticaria) within 7 days after any study injection• SAE that is assessed by the investigator as possibly related, or for which there is no alternative, plausible, attributable cause 
Safety data will be monitored on an ongoing basis by the site investigators and sponsor in order to promptly identify and flag any event that potentially contributes to a

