10.7 Safety Monitoring and Study Stopping Rules

Stopping rules are proposed as conditions that would stop further vaccinations in an individual subject (at any dose level) if they experience any of the following events that are assessed as possibly related by the investigator, or for which there is no alternative, plausible, attributable cause:

- Fever >40.0°C (>104.0°F) for at least 1 daily measurement within 7 days after vaccination
- Any grade 4 or life-threatening event within 7 days after any study injection, regardless of relationship to study vaccine
- Clinically significant systemic reaction (i.e., angioedema, generalized urticaria) within 7 days after any study injection
- SAE that is assessed by the investigator as possibly related, or for which there is no alternative, plausible, attributable cause

Safety data will be monitored on an ongoing basis by the site investigators and sponsor in order to promptly identify and flag any event that potentially contributes to a stopping rule. If the DSMB recommends unblinding of individual cases, data from placebo recipients will not contribute to the stopping rules.

Study randomization and further vaccinations will stop if 2 or more participants receiving VBI-2902a or VBI-2905a meet stopping rules unless the DSMB and study sponsor and site investigators review the safety data, and in consultation with the appropriate regulatory authorities, determine that safety of study participants is not affected and that study vaccination may continue.

If any of these safety signals are met at any point during the study, the result of the discussions by the DSMB will be communicated by the Sponsor designate to the study centers and the regulatory authorities.

An investigator who identifies any safety concern (i.e., meeting of stopping rules or any other safety concern) should inform the Medical Director at the study CRO immediately, and further enrollment may be put on hold as a consequence.

Of note, no formal stopping rule will be applied for other safety data such as missed visits due to product-related AEs, Grade 2 AEs and AEs collected from Day 7 to Day 29 after injection. However, the

DSMB will review these data, if available, in order to allow for an overall assessment of the benefit to risk.

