2 STUDY OBJECTIVES AND ENDPOINTS

Phase 1a	
Primary Objectives:	Primary Endpoints:
To evaluate the safety and tolerability of VBI-2902a containing 5 µg of S protein in one- or two-dose regimens in previously unvaccinated healthy adults of 18-54 years of age.	
 Rate and severity of local and systemic solicited adverse events (AEs) during 7 days after each study vaccination Rate and severity of unsolicited AEs during 28 days after each study vaccination Rate and severity of medically-attended adverse events (MAAEs) during 28 days after each study vaccination Rate of serious adverse events (SAEs) at during 28 days after each study vaccination AEs leading to discontinuation of study vaccination AEs leading to study discontinuation Rate and severity of laboratory abnormalities (hematology, biochemistry, urinalysis) during 28 days after each study vaccination
Secondary Objective:	Secondary Endpoints: 
 Rate and severity of unsolicited AEs throughout the study Rate and severity of medically-attended adverse events (MAAEs) throughout the study Rate of serious adverse events (SAEs) throughout the study Rate and severity of laboratory abnormalities (hematology, biochemistry, urinalysis) throughout the study GMT and the geometric mean fold increase in serum antibody titer post-vaccination over Day 1 (baseline) at Days 7, 28, 35, 56, 112,

	
224 and 336 (Phase 1a, groups G1, G2 and G3);
 
 ○ Neutralizing activity against spike protein-expressing pseudovirus, and/or PRNT neutralizing activity against wild-type SARS-CoV-2 virus and other variants of concern ○ RBD Antibody titers against wild-type variant spike protein measured by ELISA
Exploratory Objectives	Exploratory Endpoints
Phase 1b	
Primary Objective:	
Endpoints:
 
 • Rate and severity of local and systemic solicited adverse events (AEs) during 7 days after each study vaccination • Rate and severity of unsolicited AEs during 28 days after each study vaccination • Rate and severity of medically-attended adverse events (MAAEs) during 28 days after each study vaccination • Rate of serious adverse events (SAEs) at during 28 days after each study vaccination • AEs leading to discontinuation of study vaccination • AEs leading to study discontinuation • Rate and severity of laboratory abnormalities (hematology, biochemistry, urinalysis) during 28 days after each study vaccination

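### The SAP counts only unsolicited SAEs, MAAEs and AE discontinuations, although the endpoints cover all AEs, so some solicited reactions drop out of these rates

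*SAP*

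**What the plan says.** SAP 6.3.1.2 lists the rows of the TEAE overview table. Five of them carry the restriction:

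- item e: "With any unsolicited MAAEs at Day 56 and 28 days after each vaccination dose"
- item f: "With any unsolicited SAEs at Day 56 and 28 days after vaccination dose"
- item g: "With any unsolicited AEs leading to discontinuation of study vaccination"
- item h: "With any unsolicited AEs leading to study discontinuation"
- item j: "With any unsolicited SAEs during the study"

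The same section builds SOC/PT summaries from this list, leaving out only the two solicited rows (b and c). It refers to the list as point 2 although it is numbered 1; the letters match, so I read it as the same list.

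The endpoints have no such limit. SAP 2 states one of them as "AEs leading to discontinuation of study vaccination", and it states the SAE, MAAE and study-discontinuation endpoints equally without restriction. Protocol 4.10 and 10.1.1 agree. In the same lists, the general AE endpoint is limited to unsolicited events, so the authors used the word where they meant it.

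The Protocol glossary treats an AE as unsolicited if it is reported in addition to the solicited ones, or if it is a solicited symptom that starts outside the solicited period. Protocol 8.1 adds that a reaction lasting beyond Day 7 is also recorded as an AE. SAP 7 states that the planned analyses are unchanged from the protocol.

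**The concern.** Safety is the primary objective in both phases. The SAE, MAAE and discontinuation rates during the 28 days after vaccination are primary endpoints, and the whole-study SAE rate (item j) is secondary. As written, the rows for these endpoints estimate something narrower. The events left out are solicited reactions severe enough to need medical care, to be serious or to end participation, and a reader of a reactogenicity-focused first-in-human study would look for exactly these.

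The class is foreseeable. In Protocol Tables 5 and 6, Grade 4 pain, tenderness, headache, fatigue, myalgia or diarrhea is defined by emergency care or hospital admission. Under Protocol 8.1, emergency care is a route to an MAAE and admission is a route to an SAE. The overview table could then show zero SAEs in a group whose SAE listing contains a case.

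**Working it through.** **Step 1. Endpoint against planned output.**

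| Endpoint (Protocol 4.10, SAP 2) | Row in SAP 6.3.1.2 | Other planned output covering all events |
|---|---|---|
| MAAEs, 28 days after each dose | e, unsolicited only | no rate; no separate listing in SAP 6.3.1.3 |
| SAEs, 28 days after each dose | f, unsolicited only | no rate; listing of all SAEs |
| SAEs, whole study | j, unsolicited only | no rate; listing of all SAEs |
| AEs ending vaccination | g, unsolicited only | disposition reasons (SAP 6.1.1); listing |
| AEs ending study participation | h, unsolicited only | disposition reasons (SAP 6.1.1); listing |

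**Step 2. Trace one hypothetical participant.** Suppose a G2 participant has a severe headache on Day 3 after dose 1, is admitted, recovers by Day 6, has the event recorded as headache, and gets no second dose because of it.

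- Onset is inside the solicited window, so under the glossary the event is solicited.
- It ends before Day 7, so Protocol 8.1 does not re-record it.
- The participant is counted in item a (any TEAE) and item c (systemic solicited), and in the Grade 4 cell for headache in the solicited tables.
- The participant is not counted in e, f, g or j, although the event is medically attended, serious and ended vaccination. Had the participant also left the study because of it, item h would miss that too.

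**Step 3. When the event would be counted.** Two routes lead into the unsolicited rows: persistence beyond Day 7 (Protocol 8.1), or recording under a diagnosis that is not a solicited term (Protocol 8.5). No text reclassifies a solicited reaction merely because it is serious, medically attended or leads to discontinuation.

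**Step 4. Size of one omission.** No figure in the plan is in dispute. The planned safety denominators reproduce: 20 + 20 + 27 = 67 active and 20 + 27 = 47 placebo, matching Protocol 4.4. With x omitted participants in a group of n, the row shows 0/n instead of x/n. The intervals are exact (Clopper-Pearson) 95%.

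| Group | Row as planned | All-event rate, x = 1 | All-event rate, x = 2 |
|---|---|---|---|
| G1 or G2, n = 20 | 0/20 = 0% (0 to 16.8) | 1/20 = 5.0% (0.1 to 24.9) | 2/20 = 10.0% (1.2 to 31.7) |
| G4, n = 27 | 0/27 = 0% (0 to 12.8) | 1/27 = 3.7% (0.1 to 19.0) | 2/27 = 7.4% (0.9 to 24.3) |

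The table assumes that no other participant in the group has a qualifying event. The G4 figures apply to items e, f, h and j. Item g cannot be affected there, because after a single dose no vaccination remains to be stopped. In Phase 1a, item g is affected only by reactions after dose 1.

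**The case against.** The strongest reply is that the events are not hidden.

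- SAP 6.1.1 counts participants who stop vaccination or the study, with reasons. Protocol 9.2 and 9.3 give AE/SAE as a reason without a solicited split, and SAP 5.1 presents summary tables by treatment group.
- Grade 4 solicited reactions have a rate in the solicited severity tables.
- The listings of SAEs and of AEs leading to discontinuation are unrestricted, and so are the pivot tables for the first DSMB review (SAP 6). With 20 to 27 per group, a reader can count cases from a listing.
- The table shells are in a separate document and might differ from the SAP text.

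Much of this stands for discontinuations, where the gap is partial. It does not stand for SAEs and MAAEs. A Grade 4 cell does not separate emergency care from admission and misses lower-grade reactions that were medically attended. A listing gives no rate, and MAAEs have no separate listing. Shells that differ from the SAP would themselves need reconciling.

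Three stronger readings are tempting and are not supported.

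- A reader might infer that the omitted class is the main stopping-rule event, because the synopsis names "Grade 4 local (injection site) or systemic solicited AE within 7 days after any study injection" and Protocol 10.7 includes "Fever >40.0°C (>104.0°F) for at least 1 daily measurement within 7 days after vaccination". The documents do not rank the criteria. Protocol 10.7 and SAP 5.5.1 have no separate solicited criterion, and other criteria cover systemic reactions and related SAEs.
- A reader might infer that omissions could mask the two-participant stopping threshold. That rule runs on continuous case flagging and DSMB review under a separate DSMB SAP, and nothing makes the 6.3.1.2 tables its input.
- A reader might infer that every serious or medically attended solicited reaction is lost. The two routes in step 3 of the working show otherwise, and the number affected depends on eCRF practice.

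**Conclusion.** The mismatch is real and the rows are wrong as written: items e, f, g, h and j and their SOC/PT tables do not estimate the endpoints in Protocol 4.10 and 10.1.1 and SAP 2. It matters most for SAEs and MAAEs and less for discontinuations.

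Each omitted participant removes 5.0 percentage points from the displayed rate in G1 or G2 and 3.7 points in G4. How many would be omitted cannot be derived from the documents and may be none. The conclusion assumes that the SAP applies the Protocol's definition of unsolicited and that the table shells follow the SAP text. One might expect the omissions to fall mainly on the vaccine groups, since the placebo is saline without adjuvant, but the documents give no reactogenicity rate from which to size that imbalance.

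**What to change.** Delete the word unsolicited from SAP 6.3.1.2 items e, f, g, h and j and from the matching SOC/PT tables, and keep it only in items d and i. Alternatively, add all-event rows for MAAEs, SAEs and both kinds of discontinuation, split by solicited and unsolicited. State in the SAP that a solicited event meeting any of these criteria appears in the SOC/PT tables under its MedDRA term, counted once per participant.

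The cost is a wording change and a programming filter, with no added visits or samples. One check is needed: the eCRF must link seriousness, medical attention, action taken and withdrawal to solicited events. Protocol 8.6 already asks about medical attention for each symptom, and Protocol 10.7.1 already requires the other items for each AE.
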